STUDY PROTOCOL

QUANTIFICATION OF DICLOFENAC 2.32 % (VOLTAREN) IN RINSE WATER AFTER DIFFERENT APPLICATION METHODS

Sponsor Name and Legal Registered Address	Haleon (UK) [name]
Sponsor contact	PPD
Sponsor study no./ order no.	300272
Study site	SGS proderm GmbH, Schenefeld/Hamburg, Germany
Principal Investigator	Dr. rer. nat. [name], Manager Study Operations / Investigations
Investigator	PPD
CCI	
Test date(s)	March 26 to April 11, 2025

OBJECTIVE

The aim of the exploratory study is to quantify the amount of diclofenac in rinse water after application of the test product containing 23,2 mg/g Diclofenac-N-Ethylethanamin (Voltaren® Schmerzgel forte; 2,32 %) either by hand or using an applicator and subsequent washing and/or wiping.

For this study female and male participants with healthy skin on the elbows and hands will be enrolled. The amount of diclofenac in the water will be assessed after three different washing methods, with and without use of an applicator in a cross over design.

The study will be reviewed by an independent institutional review board (IRB) for ethical approval.

ASSESSMENT

The following assessment(s) will be performed:

- Voltaren® Schmerzgel forte; 2,32 % (Diclofenac) in water [mg/l]
- Amount of test product residues by gravimetrical measurements [mg]

TYPE OF PRODUCT(S)

- Voltaren® Schmerzgel forte; 2,32 % with and without applicator (Pain Gel (Medicinal Product))

STUDY DESIGN

- Exploratory
- Open labeled
- Cross over

TYPE OF STATISTICS

- Comparison between all water samples
- Descriptive statistics for all water samples

ASSESSMENT TIMES

After test product application and washing for Diclofenac concentration:

Method 1 = W01 (Hands), W02 (Elbow)

Method 2 = W03 (1st washing of elbow), W04 (2nd washing of elbow)

Method 3 = W05 (Hands and elbow)

For amount of test product residues by gravimetric measurements:

Method 3

TEST MATERIALS

Code/Study site	Product/Code/Sponsor/Concentration
A	Voltaren® Schmerzgel forte with and without Racetrack applicator

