The test material(s) will be a commercially available over the counter drug, which will be used according to package leaflet and will be provided by the study site. Test materials will be identified by a study site code (e.g. "A", "B" etc.) The test materials will be stored at room temperature in the containers in which they are received unless otherwise specified. Test material remaining at the conclusion of the study will be destroyed at least 6 weeks after issuance of the final report unless requested otherwise.

TEST AREA

Elbow (for test product application)

Hands (for washing sequence)

ASSIGNMENT OF TEST AREAS

The left or right elbow will be used, depending on the handedness of the participant; i. e. in case of a right handed participant, test area will be on the left side and vice versa.

APPLICATION VOLUME

Pea-sized amount as per label (the test product will be weighed before and after usage)

APPLICATION MODE

Participants will wash their hands and the test area prior to product application with water and soap according to normal use conditions of the participant to avoid any contamination of the samples.

The test product will be applied by the participant depending on the method:

Method 1: application with one hand by gently massaging in for 60 seconds

Method 2 and method 3: application with the applicator without involving the hand and by gently massaging in with the applicator for 60 seconds.

ACCIDENTAL EXPOSURE TO Voltaren® Schmerzgel forte; 2,32 %

All study participants will be instructed to notify the study staff if they are accidentally exposed to Voltaren® Schmerzgel forte; 2,32 %. In the event that a study participant gets product on their skin, the product should be washed off. In the event that a study participant gets the product in their eyes, the participant should rinse their eyes thoroughly with clean water.

WASHING PROCEDURE

After application, enough water to wetting the participants hands or test area will be poured slowly over the hands or test area by a technician. Afterwards approx.1 mL soap (Bode Baktolin® pure Waschlotion) is massaged into the entire palm and outer surface of the hands or the test area by the participant for about 10 seconds. Then the soap will be rinsed off by the technician slowly pouring 2 litres of lukewarm water (35°C +/- 2°C) for approximately 30 seconds over the hands and/or test area ensuring no soap residues are visible on the skin. All water used for the washing procedure will be

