Method 2: The participants will return to the study site and the test product will be applied with the applicator (see application mode). 5 minutes after application, participants will wash the test area according to the washing procedure. This will be repeated after 5 minutes. The water of each washing step (1st and 2nd washing of test area) will be caught separately in a jar and handled as described below (see investigational methods). The test product will be weighed before and after application.

Any remaining test product on the elbow and the hands will be removed using alcohol on a paper towel by the participants themselves.

Method 2

Method 3: The participants will return to the study site and the test product will be applied with the applicator (see application mode). 5 minutes after application, participants will wipe the test area with a paper towel. Afterwards, the test area and hands will be washed according to the washing procedure. The water of the washing step will be caught in a jar and handled as described below (see investigational methods).

The paper towels and test product will be weighed before and after application. Any remaining test product on the elbow and the hands will be removed using alcohol on a paper towel by the participants themselves.

Method 3

As a wash out period, a time frame of at least 2 days will be kept in between each method per participant. No carry over effect of the test product is to be expected due to this washout periods.

CLIMATIC CONDITIONS

During the investigation(s) room temperatures without additional air conditioning will be used.

TEST SCHEDULE

A scheme of the test procedure is given as appendix 1 to protocol.

INVESTIGATIONAL METHOD(S)

The following investigational method(s) will be performed:

TAKING OF WATER SAMPLES for lab analysis

- The water used for the washing sequence will be caught in a jar and will be stirred for 1 minute. Afterwards 3 water samples (approx. 100 ml) will be taken from different locations in the jar (top, bottom and in the middle) with tubes provided by the laboratory.
- A control sample of tap water only, collected prior to the product application, will also be analysed to prove the absence of diclofenac in the tap water used for washing.
- To minimize sample cross-contamination, a fresh pair of gloves will be worn by the technician for each participant.
- Water samples will be stored at room temperature until shipment.

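### The objective is an amount of diclofenac, but only mg/l per jar is analysed; volumes are not recorded, the Method 3 volume is unclear and no total per method is calculated

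*Combined protocol and SAP*

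**What the plan says.** The Objective section names a mass: "The aim of the exploratory study is to quantify the amount of diclofenac in rinse water". The Assessment section then lists the diclofenac variable in mg/l. Under Analysis of Data, the three readings from each jar are averaged. That mean concentration is the raw datum for the tables, the bar charts and the paired t-tests between all water samples.

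The Washing Procedure has three parts that bear on volume:

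- Wetting: "enough water to wetting the participants hands or test area will be poured slowly", with no volume given.
- Soap: "Afterwards approx.1 mL soap".
- Rinse: "slowly pouring 2 litres of lukewarm water (35°C +/- 2°C) for approximately 30 seconds over the hands and/or test area", continued until no soap is visible. The text does not say what happens if soap is still visible after 2 litres.

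The section closes with "All water used for the washing procedure will be" collected.

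Under Test Procedure, Method 1 fills two jars (W01 hands, W02 elbow) and Method 2 fills two (W03 and W04, first and second elbow wash). Method 3 fills one (W05): "Afterwards, the test area and hands will be washed according to the washing procedure". The sampling steps under Investigational Method(s) cover stirring, sampling, a tap-water control, gloves and storage, but not volume. The product is weighed, and in Method 3 the paper towels too. No section says that the water is weighed or measured, that mg/l is converted to mg, or that the jars of a method are added up.

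**The concern.** Concentration is mass divided by volume. It can stand in for mass only if every jar holds the same volume, and jar results can stand in for a method only if each method's jars are added up. The plan secures neither fully.

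Two things are at stake. First, the stated objective, an amount for each of three methods, is not an output of the planned analysis. Second, a test of W05 against W01, W02, W03 or W04 sets the whole washed-off quantity of one method against part of another's, in a jar whose volume the text leaves open. A significant result could reflect the number of jars or the rinse volume rather than the use of an applicator or wiping.

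There is a further loss. Towel residue in Method 3 is assessed in mg. Without a volume for W05, wiped-off and washed-off quantities cannot be put on one scale or related to the weighed product applied.

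**Working it through.** The plan gives no sample size or power figure to reproduce. The check is a mass balance.

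**Inputs.** From the Washing Procedure: rinse 2 L and soap about 0.001 L per washing procedure. From Test Procedure: two jars each in Methods 1 and 2, one jar in Method 3. The wetting volume *v* is not in the documents. It is assumed here and varied from 0.1 to 0.5 L per washed site.

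**Formula.** Volume of a jar with one washing procedure = 2 + 0.001 + *v*. Concentration = mass / volume.

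**Step 1: single jars, W01 to W04.** For equal mass and different wetting volumes, the concentration ratio is the inverse ratio of volumes:

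- 0.1 against 0.2 L: 2.201 / 2.101 = 1.05
- 0.1 against 0.3 L: 2.301 / 2.101 = 1.10
- 0.1 against 0.5 L: 2.501 / 2.101 = 1.19

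If mg were later calculated as concentration × 2 L, mass would be understated by 1 − 2/2.101 = 4.8% at *v* = 0.1 L, 1 − 2/2.201 = 9.1% at 0.2 L, and 1 − 2/2.501 = 20.0% at 0.5 L.

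**Step 2: methods.** Take the same total washed-off mass in Methods 1 and 3, 10 mg for illustration, with *v* = 0.1 L per site.

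| Jar | Mass | Volume | Concentration |
|---|---|---|---|
| W01 and W02, even split | 5 mg each | 2.101 L each | 2.38 mg/l each |
| W05, one 2 L rinse, two sites wetted | 10 mg | 2.201 L | 4.54 mg/l |
| W05, two 2 L rinses | 10 mg | 4.202 L | 2.38 mg/l |

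- One rinse: W05 / W01 = 4.54 / 2.38 = 1.91, about two-fold, although the methods released the same total.
- Two rinses: W05 equals W01 at 2.38 mg/l, although W05 holds twice the mass. Put the other way, the same 5 mg in each jar reads 5 / 4.202 = 1.19 mg/l in W05 against 2.38 mg/l in W01, a ratio of one half.

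The ratio also depends on how Method 1 divides between its jars. With one rinse and a 90:10 split, the two Method 1 jars read 4.28 and 0.48 mg/l, so W05 is 1.06 times one and about 9.5 times the other, again with equal totals.

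**Step 3: what the planned tests compare.** Five samples give 5 × 4 / 2 = 10 pairs. Two pairs lie within a method (W01–W02, W03–W04). Four set part of Method 1 against part of Method 2. Four set part of Method 1 or 2 against the whole of Method 3. None compares the totals of two methods.

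**The case against.** The best defence is that the plan controls most of the volume. Each washing procedure has a fixed 2 L rinse, and all water is collected. W01 to W04 therefore share one nominal volume, and mg/l is nearly proportional to mg among them. Every jar receives wetting water and the tests are paired, so a common wetting volume cancels and only differences matter. This stands. A reader might infer that mg/l cannot be compared between methods at all; for the jars of Methods 1 and 2 the documents do not support that.

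A reader might also infer that pooling the Method 1 water (about 4 L) and comparing it with W05 (about 2 L) would produce a false two-fold difference in the planned analysis. It would not, because the plan never pools Method 1 water. Under the one-rinse reading, the W01 and W02 concentrations add to 4.76 mg/l against 4.54 mg/l in W05, a ratio of 1.05. The two-fold effect belongs to the single-jar tests that the plan does specify.

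The defence can also say that one washing step and one jar in Method 3 suggest a single 2 L rinse, and that "over the hands and/or test area ensuring no soap residues are visible on the skin" provides for a joint wash. That is a reasonable reading, but the text does not fix it, and under it W05 still holds a whole method while the other jars hold parts.

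Finally, the study is exploratory and mg/l is its declared assessment; nominal mg could be derived afterwards. This lowers the urgency, but it does not explain why the quantity in the objective is not planned as a result. It is also possible that the CRF or the appended test scheme, neither of which is in the text available, records volumes. The claim here is only that no section says so.

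**Conclusion.** The point holds in a limited form. The objective is an amount after each of three methods, and the planned analysis does not deliver it.

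For single jars in Methods 1 and 2 the consequence is modest: a shift of about 5% (0.1 against 0.2 L) to 19% (0.1 against 0.5 L) in a jar-to-jar ratio. Both wetting ranges are assumptions. If hands regularly take more wetting water than an elbow, which is an inference, the shift is systematic rather than random.

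At method level the consequence is larger. With equal totals split evenly, W05 reads about twice W01 or W02 if one 2 L rinse is used; if two are used, the same mass per jar reads about half in W05. The even split and the 10 mg total are illustrative. The 10 mg does not affect the ratios, but the split does.

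**What to change.** 1. Record the total water for every jar, either as wetting plus rinse volume poured or by weighing the jar empty and full before any sample is drawn. State which is used: if mixed water is lost by splashing, the collected volume understates mass, whereas the poured volume does not.
2. Calculate mg = mean concentration × volume for each jar.
3. Sum within method: W01 + W02, W03 + W04, and W05 alone.
4. Make the paired between-method comparisons on these mg totals, and keep mg/l per jar as supporting data.
5. State the rinse volume and soap amount for the combined hands-and-elbow wash in Method 3, and what is done if soap remains visible after 2 L.

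The test dates given are March 26 to April 11, 2025. If collection is complete, document the volume actually used in Method 3 and report mg from nominal volumes with a stated uncertainty range.

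The cost is about 33 × 5 = 165 volume records, one CRF field and a little more analysis.

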collected.

STUDY POPULATION

A minimum of 33 participants will be recruited for this test from the general population and neighbouring communities of the study site's location so that about 30 participants are expected to finish in the study. Participants who drop-out after randomization into the study will not be replaced. All participants will have a complete understanding of the test procedure.

All below mentioned inclusion, exclusion criteria and instructions for the participants will be checked by a questionnaire before the start of the study and during the study. Conditions developing during the study listed in the exclusion criteria and instructions as well as protocol deviations do not necessarily lead to the participant's exclusion. The investigator decides whether the participant is still eligible.

INCLUSION CRITERIA

- Written informed consent to participate in the study
- Willingness to actively participate in the study and to come to the scheduled visits
- Female and/or male
- From 18 to 70 years of age

EXCLUSION CRITERIA

- Female participants: Pregnancy or lactation
- Drug addicts, alcoholics
- AIDS, HIV-positive or infectious hepatitis
- Conditions which exclude a participation or might influence the test reaction/evaluation
- Participation or being in the waiting period after participation in cosmetic and/or pharmaceutical studies pertaining to the test area
- Cancer not being diagnosed as cured and requiring chemotherapy, irradiation and/or hormonal treatment within the last 2 years
- A previous allergic reaction, sensitivity or intolerance to diclofenac or any of the other ingredients in Voltaren® Schmerzgel forte
- Patients in whom asthma, angioedema, urticaria or acute rhinitis are precipitated by acetyl salicylic acid or other non-steroidal anti-inflammatory drugs (e.g., ibuprofen, naproxen etc.)
- Documented allergies to cosmetic products
- Active skin disease at the test area
- Wounds, moles, tattoos, scars, irritated skin, excessive hair growth, etc. at the test area that could influence the investigation
- Any topical medication at the test area within the last 3 days prior to the start of the study

INSTRUCTIONS FOR PARTICIPANTS

Instructions prior to the start of the study:

The participants will be instructed not to...

- Not applicable

The participants will be instructed to...

- Not applicable

Instructions throughout the course of the study:

The participants will be instructed not to...

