- apply any products with the same indication as the test product to the test area throughout the entire course of the study

The participants will be instructed to...

- Not applicable

INFORMED CONSENT

For studies with participants the following procedure will be effective: Each participant must provide the investigator/investigator's designee with written informed consent prior to enrollment in the study. The participants will be provided with a signed copy of the informed consent statement.

The original signed copy for each participant in the study will be retained in the investigator's study records. The consent statement shall meet the requirements of any applicable regulation. The investigator or the investigator's designee will inform each participant as to the purpose and nature of the study in compliance with applicable regulations.

The participants are informed that they can withdraw their consent at any time and that they can stop their participation in this study at any time, without disadvantages. They are also informed that the study site can also prematurely terminate their participation in the study, for example for administrative reasons.

[figure not shown]
TEST PROCEDURE

The order of the methods will be to the following for all participants:

Method 1: The participants will come to the study site. They will be informed about the study and give their written consent. Then, the test product will be issued to the participants with instructions to use them on the assigned test area (see application mode). The assignment of the test area will be done according to handedness of the participants. After the application of the test product with one hand, participants will wash their hands according to the washing procedure. 5 minutes after application, participants will wash the test area according to the washing procedure. The water of each washing step (hand and test area) will be caught separately in a jar and handled as described below (see investigational methods). The test product will be weighed before and after application.

Any remaining test product on the elbow and the hands will be removed using alcohol on a paper towel by the participants themselves.

[figure not shown]
Method 1

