- The samples will be shipped after the end of each study day to the following address:

- The labeling of the tubes will be as following:

Study Number: CCI

SXXW0X

- Participant No.: XX = 01-33
- Water Sample: W01= Method 1- Hands, W02= Method 1 - Test area,
W03= Method 2 - 1st washing, W04= Method 2 – 2nd washing,
W05= Method 3

Water sample analysis regarding the amount of diclofenac with HPLC will be performed by an external partner laboratory:

The analysis will be performed according to the following steps:

Determination of Diclofenac amount by direct injection:

- If necessary: filtration of the samples through 0.45 µm PTFE (Polytetrafluorethylene) filter.
- Addition of an isotope-labelled standard
- Direct injection and measurement by RP-LC-MS/MS (reverse phase-liquid chromatography–mass spectrometry) in positive ionization mode.

The laboratory will destroy the samples and/or remaining material and document the destruction. The laboratory will provide the study site with a document to confirm the destruction. The destruction will take place 6 weeks after sending the results at the very latest.

ADVERSE EVENT

The investigator and any qualified designees are responsible for detecting, documenting, and reporting events that meet the definition of an adverse event (AE) or serious adverse event (SAE).

Definitions

Adverse Event (AE): An AE is any untoward medical occurrence in a clinical study subject, temporally associated with the use of a study product, including any washout or lead-in product (or medical device), whether or not considered related to the study product.

Serious Adverse Event (SAE): An SAE is any untoward medical occurrence at any dose that results in death, is life-threatening, requires inpatient hospitalization or prolongation of existing hospitalization, results in persistent or significant disability/incapacity, results in congenital anomaly/birth defect, or is otherwise considered an important medical event.

Time Period for Collecting Adverse Event Information

All AEs and SAEs will be collected immediately after a subject provides consent to participate in the study (i.e., by the completion of the ICF) and up until 5 days following last administration of test product (if reported by the subjects).

Recording Adverse Event Information

All AEs and SAEs will be recorded on the AE page of the CRF by the investigator or site staff. AEs should be reported using concise medical terminology.

Reporting of Serious Adverse Events

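### All participants take Methods 1, 2 and 3 in the same order, so the between-method comparisons cannot be separated from visit

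*Combined protocol and SAP*

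**What the plan says.** The Objective describes three washing methods compared "with and without use of an applicator in a cross over design", and Study Design also lists cross over. Test Procedure then says "The order of the methods will be to the following for all participants" and sets out Method 1, Method 2 and Method 3 in turn. The later methods take place at return visits; for example, "Method 2: The participants will return to the study site and the test product will be applied with the applicator". The gap between visits has a minimum only: "As a wash out period, a time frame of at least 2 days will be kept in between each method per participant". On carry-over the protocol says "No carry over effect of the test product is to be expected due to this washout periods".

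Study Population refers to randomisation ("Participants who drop-out after randomization into the study will not be replaced"), but no randomised element is described anywhere, and Analysis of Data marks derandomisation as not applicable. The elbow is fixed by handedness, so it is not randomised either.

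Statistical Data Analysis plans paired t-tests between all pairs of water samples at alpha 0.05, without multiplicity adjustment. There is no visit, period, sequence or date term.

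**The concern.** A cross-over protects a within-participant comparison from time effects only if the order varies between participants. Here Method 1 is always first and Method 3 always last. Whatever changes between visits is added to the method difference, and the paired t-test reads the sum as a method effect.

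Some change is plausible. Participants dispense, massage and lather themselves, and they learn the washing routine at Method 1. The applicator is first used at Method 2 and used again at Method 3, so the comparison of washing alone with wiping then washing is also a comparison of first with second applicator use. Technicians pour and collect by hand, and the rooms have no additional air conditioning.

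At stake is the attribution of differences between hand and applicator, and between washing and wiping. The plan intends to test both.

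**Working it through.** The plan states no power or sample-size figure on this point, so there is none to reproduce. The check has three parts.

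**1. Which comparisons are affected.** Five samples give 5 × 4 / 2 = 10 pairs. W01 with W02 (both Method 1) and W03 with W04 (both Method 2) lie within one visit. The other 10 − 2 = 8 pairs compare different methods at different visits.

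**2. Whether any model can separate method from visit.** Take 30 completers (Study Population expects about 30) and a linear model with 30 participant columns, 2 method contrasts and 2 visit contrasts, 34 columns in all.

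- Fixed order: rank 32 of 34. The two method contrasts are identical to the two visit contrasts.
- All six orders, 5 participants each: rank 34 of 34. Method can be estimated separately from visit.
- The variance of a visit-adjusted method difference with six balanced orders is 0.0667σ². The simple paired difference has 2σ²/30 = 0.0667σ². Balancing loses no precision on this measure.

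**3. What a drift would do to the planned test.** The documents give neither a CV nor a drift, so these are assumptions: lognormal data, between-participant CV 40%, no true method difference, mean multiplied by f = 0.90 from one visit to the next, and a two-sided test (sidedness is not stated). With the first-visit mean set to 1:

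- Variance of the paired difference = (1 + 0.40²) × CV² × (1 + f²) + (1 − f)² × 0.40² = 1.16 × CV² × 1.81 + 0.0016.
- Standardised shift δ = 0.10 / SD of the difference.
- Rejection probability = P(|T| > 2.045), where T is noncentral t with 29 degrees of freedom and noncentrality δ√30.

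| Within-participant CV (assumed) | SD of difference | δ | Rejection, noncentral t | Rejection, simulated on the raw scale |
|---|---|---|---|---|
| 20% | 0.293 | 0.342 | 44% | 45% |
| 40% | 0.581 | 0.172 | 15% | 15% |
| 60% | 0.870 | 0.115 | 9% | 9% |

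The simulation used 100,000 studies per row. At CV 40%, simulated drifts of 5%, 10%, 15% and 20% give rejection in about 7%, 15%, 30% and 50% of studies. Method 1 and Method 3 are two visits apart. If a 10% drift compounds (0.90² = 0.81), rejection at CV 40% is about 46%.

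With balanced orders the bias from a linear drift averages to about zero. An unadjusted paired t-test then becomes conservative: with drifts of 0.2, 0.5 and 1.0 SD of the paired difference per visit, it rejects in 4.3%, 1.7% and 0.1% of simulated studies. That is why a period term is needed as well as balance.

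**The case against.** The strongest defence has five parts.

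- *The study is exploratory and aims to quantify.* The per-sample summaries and the two within-visit comparisons involve no between-visit contrast, and a very large method difference could exceed any plausible drift. This stands. It does not cover the between-method t-tests, which are planned at alpha 0.05.
- *The procedure is scripted.* Massage time, soap volume, lathering time, and rinse volume, temperature and duration are all specified. This limits learning but does not exclude it.
- *Existing data help.* The product is weighed at every application, so a drift in dispensed amount could be examined. If gaps between visits vary, a linear calendar-date trend could also be estimated. Neither analysis is planned, and neither separates method from visit number itself.
- *Carry-over.* A reader might infer that residue biases Methods 2 and 3. Carry-over can fall only on those methods and cannot be separated from method. But residue would have to survive a soap wash with a 2-litre rinse, an alcohol wipe, at least 2 days and a soap wash before the next application. The documents do not show that it is material. The claim of none is nevertheless untested, because the control sample is tap water and not a skin rinse. The minimum gap is also shorter than the interval in the exclusion criterion "Any topical medication at the test area within the last 3 days prior to the start of the study". The two should be reconciled or the difference explained.
- *Assay date.* A reader might infer from "The samples will be shipped after the end of each study day to the following address" that laboratory date moves with method. The documents give the shipping day, not the analysis day. The laboratory could run a participant's samples together, and the isotope-labelled standard limits assay drift.

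A reason for the fixed order might appear in the test-schedule appendix, which was not available for this check.

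**Conclusion.** The point holds. The fixed order aliases method with visit completely in 8 of the 10 planned comparisons, and this does not depend on any assumed figure. The consequence for the p-values does: a 10% drift raises the false-positive rate from 5% to about 45%, 15% or 9% as the assumed within-participant CV goes from 20% to 40% to 60%. Those figures show how sensitive the test is. They are not evidence that such a drift will occur.

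It would go too far to conclude that the study's results as a whole are invalid, or that carry-over or assay date is an established bias. The documents support neither reading. This should be fixed: it limits attribution of between-method differences, and the remedy is cheap.

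**What to change.** Randomise participants to the six orders of Methods 1 to 3 in balanced numbers. For 33 participants that means 5 or 6 per order (3 × 6 + 3 × 5 = 33), with consent taken at whichever visit comes first. Analyse the between-method contrasts with method and period as fixed effects and participant as a random effect. The paired t-test can remain for W01 with W02 and W03 with W04.

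The cost is a randomisation list, a protocol amendment and having all three procedures ready on each study day. No extra participants, visits or samples are needed.

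If the order must stay fixed, or data collection has already begun, remove the cross-over label and the reference to randomisation, and report the between-method p-values as confounded with visit. In either case, stating the laboratory's analysis dates would settle the assay question.

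### Gloves are changed per participant and other products are restricted only at the test area, leaving two contamination routes that the tap-water control could not show and that are cheap to close

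*Combined protocol and SAP*

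**What the plan says.** Under INVESTIGATIONAL METHOD(S), the control is "A control sample of tap water only, collected prior to the product application", analysed "to prove the absence of diclofenac in the tap water used for washing". The labelling scheme there gives codes to W01 to W05 only, and ANALYSIS OF DATA gives the control no role.

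The same section, with the aim of limiting cross-contamination between samples, states that "a fresh pair of gloves will be worn by the technician for each participant". TEST PROCEDURE has two washes collected in separate jars in Method 1 (hands, W01; elbow, W02), two in Method 2 (first and second elbow wash, W03 and W04), and one in Method 3 (hands and elbow, W05).

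Under INSTRUCTIONS FOR PARTICIPANTS, participants are told not to "apply any products with the same indication as the test product to the test area throughout the entire course of the study". Compliance is checked by a questionnaire before and during the study (STUDY POPULATION).

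Three safeguards are planned:
- APPLICATION MODE: "Participants will wash their hands and the test area prior to product application with water and soap", in order "to avoid any contamination of the samples".
- TEST PROCEDURE: after each method, participants remove remaining product from elbow and hands with alcohol.
- TEST PROCEDURE: methods are at least 2 days apart. The plan concludes that "No carry over effect of the test product is to be expected due to this washout periods".

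**The concern.** The study measures small amounts of one substance in about 2 litres of water, and some samples are expected to hold little of it. Contamination can only add drug, so it does not average out like random error. Two routes are left open.

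The first is the gloves. The plan wants to limit transfer between samples but sets the change by participant. Within a visit, transfer could go from an earlier wash into a later one. It would be read as drug that the later wash removed from the skin.

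The second is other diclofenac products. A participant may use one on another body site, applied by hand, without clearly breaking an instruction. Hands are rinsed into W01 and W05. Participants also massage the soap in themselves during the elbow washes, so W02 to W04 are not shielded.

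A tap-water sample cannot reveal either route. The W01 to W05 means go into paired t-tests without a background check, so any such addition would be reported as a method result.

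**Working it through.** The documents give no figure to reproduce: no sample size calculation, SD, recovery or gel mass. They do give 23.2 mg diclofenac salt per g of gel, a 2-litre rinse, at least 33 recruited and about 30 finishing. Everything marked *assumed* below is illustrative.

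**1. Gloves, from the text.** Each participant has 3 visits and 5 washes. If gloves are fresh at each attendance (not spelled out), transfer is confined to W01→W02 and W03→W04. Drug left on the elbow after the first Method 2 wash is what W04 is meant to measure; only transfer by glove or jar would be an artefact.

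**2. Gloves, size.** If v ml of W03 water reaches the W04 jar, it brings v/2000 of the W03 content. The relative rise in W04 is (v/2000)/q, where q is W04 as a fraction of W03.

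| v (*assumed*) | v/2000 | q = 5% (*assumed*) | q = 1% (*assumed*) |
|---|---|---|---|
| 0.1 ml | 0.005% | 0.1% | 0.5% |
| 1 ml | 0.05% | 1% | 5% |
| 5 ml | 0.25% | 5% | 25% |

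The rise is small unless the second wash is very low or the transfer large. It would narrow the W03–W04 difference and inflate W04 against the other samples.

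**3. Other products, size.** *Assumed*: 2 g of gel rubbed into another site, 2 × 23.2 = 46.4 mg; 0.01% to 1% still on the hands after the pre-application wash, 0.00464 to 0.464 mg; study dose 0.5 g, 0.5 × 23.2 = 11.6 mg; W05 holding 5% to 20% of it, 0.58 to 2.32 mg.
- Smallest rise for that participant: 0.00464/2.32 = 0.2%.
- Largest rise: 0.464/0.58 = 80%.
- If one of 30 participants is affected at the largest value and all have the same true W05, the mean rises by 80%/30 = 2.7%.

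**4. Effect on a test.** For a two-sided paired t-test (sidedness *assumed*) at 0.05 with n = 30 and equal true means, an offset of d SDs of the paired difference in one sample only gives noncentrality d√30. The rejection rate is 5% at d = 0, 8.3% at 0.1, 18.5% at 0.2, 35.5% at 0.3 and 75.4% at 0.5. An offset equal in both samples cancels. The documents do not allow d to be estimated.

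**5. Earlier visits, direction.** The order is Method 1, 2, 3 for everyone. Residue from an earlier visit could raise only W03 to W05. It would tend to shrink an applicator advantage over Method 1, and with a fixed order it could not be separated from the method.

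**The case against.** The strongest reply is that contamination is guarded against several times over. Residue from an earlier visit would have to survive the study wash, the alcohol removal, two days or more and the soap wash before the next application. It would then have to come off in a further soap wash. This stands: between-visit carry-over is unlikely. It does not turn expectation into evidence, because the pre-application wash water is not among the coded samples and participants do the alcohol step themselves.

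On gloves, the technician pours water while the participant massages the skin, and no text has the technician touching gel or soaped skin. This too stands, and it makes large transfers hard to credit. But each jar is stirred and sampled at three depths, and the plan itself treats gloves as a transfer route.

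On other products, TEST AREA lists the hands, so the restriction arguably reaches them, and a general exclusion covers conditions that might influence the evaluation. However, WASHING PROCEDURE treats hands and test area as alternatives, and neither text addresses gel applied by hand elsewhere.

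Three stronger readings are tempting and not supported:
- A reader might see a contradiction between the 2-day washout and the exclusion for "Any topical medication at the test area within the last 3 days prior to the start of the study". The latter is an entry criterion for any product in any amount, without supervised removal. The former follows a known small application that was washed and wiped off. They serve different purposes and need not agree.
- A reader might infer that hand contamination could affect only W01 and W05. Participants massage soap into the test area themselves, so the elbow washes may be exposed too.
- A reader might call for a skin-contact blank at the Method 2 and 3 visits. With 33 participants that is 66 extra washes and assays. It would treat the skin before dosing differently from Method 1 and could not detect transfer between two washes of one visit.

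**Conclusion.** The point holds as a low-cost improvement. As written, the glove rule permits transfer from the first to the second wash of a visit, the product restriction leaves use elsewhere on the body unaddressed, and the tap-water control would show neither. A reader might go further and infer that stray diclofenac is being counted as a method result. The documents do not support that: they contain no sign that any is present, and its size cannot be calculated from them.

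The figures of 0.1% to 25% for W04 and 0.2% to 80% for one participant's W05 rest wholly on assumed inputs, and the upper ends combine the least favourable values. Samples that hold much drug would be barely affected. The low-level samples, above all W04 and possibly W05, are the ones to protect. Sample size and the planned tests do not change.

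**What to change.** 1. **INVESTIGATIONAL METHOD(S):** require fresh gloves for each washing and sampling step instead of for each participant. Counting a wash and the sampling of its jar as one step, and assuming fresh gloves at each visit now, this is 33 × (5 − 3) = 66 extra pairs.
2. **STUDY POPULATION and INSTRUCTIONS FOR PARTICIPANTS:** widen the existing questionnaire to recent use of diclofenac-containing topical products anywhere on the body, and flag affected visits in the data listings. This costs one item.
3. **TEST PROCEDURE:** word the carry-over statement as an assumption. Add that residue from an earlier visit could raise only W03 to W05 and would tend to shrink an applicator advantage over Method 1.

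A skin-contact blank is at most an optional check. If one is taken, handle it the same way in all three methods. If the visits have already taken place, state in the report how gloves were actually changed and give points 2 and 3 as limitations.
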